6.4 Study Assessments

6.4.1 Primary Assessment

The primary assessment is freedom from systemic thromboembolism or stroke: this will be as diagnosed by a physician, to include pulmonary embolism, deep vein thrombosis, and both hemorrhagic and ischemic stroke. Events relating to thromboembolism or stroke will be adjudicated using pre-determined definitions by independent committee members that remain blinded to the patient's treatment arm.

6.4.2 Secondary Assessments

- 1) Units of blood or blood products given after the first dose of anticoagulation.
- 2) Total post-operative length of stay: This will be measured from the date/time of the end of the subject's surgery until the date/time of the patient's discharge from the hospital. This will be measured in hours, to the nearest tenth of an hour.
- 3) Duration from diagnosis of post-operative atrial fibrillation (POAF) to discharge from the hospital: This will be measured from the time of the EKG that is obtained after AFib is noted on telemetry (confirming the diagnosis of AFib), until hospital discharge. This will be measured in hours, to the nearest tenth of an hour.
- 4) Time in therapeutic range of INR, if on warfarin, (eg. 2-3), measured as a percentage and defined for each patient using the Rosendaal equation
- 5) Patient compliance percentage to apixaban: measured by asking the patient to bring any unused medication to their 30-day post-operative appointment, where remaining tablets will be counted. This will be calculated as a percentage using the following

equation: (# doses prescribed - # of doses not taken and returned to investigator at follow up appointment) / # days prescribed.

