Study Objectives:	
1) Primary endpoint: freedom from stroke or thromboembolic event will be captured.
 
2) Secondary endpoints: -units of blood given after initiation of anticoagulation medication -total post-operative length of stay -duration from diagnosis of post-operative atrial fibrillation (POAF) to discharge from hospital -time in therapeutic range of INR if on warfarin -patient compliance percentage to apixaban if on apixaban
 
3) Safety assessments: major and minor bleeding events, as defined by the International Society on Thrombosis and Haemostasis, will be captured. Clinical events and blood product utilization will be identified and captured.

Study Design:	
In this open-label, prospective, randomized pilot study, patients who develop atrial fibrillation after isolated coronary artery bypass grafting surgery will be identified. Patients with persistent atrial fibrillation (>12 hours) or recurrent sustained atrial fibrillation (≥ 2 episodes of atrial fibrillation lasting longer than 30 minutes) will be candidates for inclusion. Upon meeting study inclusion and exclusion criteria, and after informed consent, patients will be randomized to either the standard of care (warfarin per protocol) or apixaban arms of the trial. Routine postoperative care after CABG will occur in both groups. Upon discharge, anticoagulation in both groups will be managed by the anticoagulation clinic. Patients will be followed for 30 days after surgery.

Accrual Goal: (Total number of subjects)	56 patients
Accrual Rate: (Number of subjects expected per month)	We anticipate enrolling 2-3 patients per month based on current projections.
FPFV: LPFV: Follow Up: (mm/dd/yy)	FPFV: 9/1/16 LPFV: 12/31/18 Follow up: 30 days per patient Final Report: 3/31/19

Correlative Studies: (PK/PD, etc.)
	
Retrospective analysis conducted at our facility:
 
Anderson E, Johnke K, Leedahl D, Dyke, C. Novel oral anticoagulants vs warfarin for the management of postoperative atrial fibrillation: clinical outcomes and cost analysis. American Journal of Surgery. Volume 210, Issue 6, 1095-1103²

Inclusion Criteria:
	
Patients diagnosed with new-onset persistent or recurrent atrial fibrillation after isolated CABG surgery. Persistent atrial fibrillation is defined as an episode of >12 hours. Recurrent atrial fibrillation is defined as 2 or more episodes of atrial fibrillation lasting longer than 30 minutes.

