2 STUDY OBJECTIVES

2.1 Primary Objective

- 1) Efficacy: Venous thromboembolism or stroke, followed until postoperative day 30.
- 2) Safety: major and minor bleeding events, followed until postoperative day 30, as defined by the International Society on Thrombosis and Haemostasis³
- 3) Clinical relevant non-major bleed.
- 4) Transfusions: units of blood or blood products given after the first dose of anticoagulation.
- 5) Total post-operative length of stay in days, defined as the time the patient leaves the operating room (day 0) until hospital discharge. Length of stay will increase by 1 day with each midnight that is passed.
- 6) Time in therapeutic range of INR, if on warfarin, (eg. 2-3), measured as a percentage and defined for each patient using the Rosendaal equation.
- 7) Patient compliance percentage to apixaban dosing, calculated as a percentage using the following equation
 - a. $(\# \text{ doses prescribed} - \# \text{ of doses not taken and returned to investigator at follow up appointment}) / \# \text{ doses prescribed}$; the follow up visit will occur after anticoagulation prescription has ended.

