5.1.1 Identification

Product Description / Class and Dosage Form	Potency	Blinded or Open Label	Packaging/ Appearance
Apixaban	5mg	Open	Pink, oval, biconvex Debossed with “894” on one side and “5” on the other side
Apixaban	2.5mg	Open	Yellow, round, biconvex Debossed with “893” on one side and “2½” on the other side
Warfarin	1mg 2mg, 2.5mg, 3mg, 4mg, 5mg, 6mg, 7.5mg, 10mg	Open	All strengths are tablets. 1mg: pink, 2mg: lavender, 2.5mg: light green, 3mg: tan, 4mg: blue, 5mg: peach, 6mg: teal, 7.5mg: yellow, 10mg: white

Medication storage:

Apixaban: Store at 20°C to 25°C (68°F-77°F); excursions permitted between 15°C and 30°C (59°F-86°F). Protect from light and moisture.

Warfarin: Store at controlled room temperature, (59°-86°F, 15°-30°C). Protect from light and moisture.

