5.4 Selection and Timing of Dose for Each Subject

Apixaban: Apixaban is to be dosed at 5 mg by mouth twice daily, except in the case of the criteria listed below in “dose modifications”. The duration of therapy will be at least 30 days. The patient’s physician may determine that anticoagulation therapy should be continued after the study period, based on their examination of the patient at the 30-day post-operative examination.

Apixaban should not be used if a patient has active pathological bleeding.

If a dose of apixaban is not taken at the scheduled time, the dose should be taken as soon as possible on the same day and then continue with twice daily administration as before. The dose should not be doubled to make up for a missed dose.

Apixaban can be taken with or without food.

Apixaban is not recommended in patients with severe hepatic impairment. No dose adjustment is recommended for patients with renal impairment alone, including those with end-stage renal disease (ESRD) maintained on hemodialysis, except nonvalvular atrial fibrillation patients who meet the criteria for dosage adjustment. Patients with ESRD (CrCl <15 mL/min) receiving or not receiving hemodialysis were not studied in clinical efficacy and safety studies with ELIQUIS; therefore, the dosing recommendations are based on pharmacokinetic and pharmacodynamic (anti-Factor Xa activity) data in subjects with ESRD maintained on dialysis.

Warfarin: While patients are hospitalized, warfarin will be dosed daily, with daily INR monitoring per hospital protocol. Daily doses may vary from 0.5mg to 15mg by mouth, as determined by patient specific factors such as patient size, hepatic function, INR, concomitant medications, diet, or other factors. Based on these factors or others not listed, there may also be days in which the patient is prescribed to not get does not receive a dose of warfarin.

After discharge from the hospital, warfarin dosing will be subsequently managed by an anticoagulation clinic, per established protocols. All patients will have a goal INR of 2-3 during the duration of the study. The duration of therapy will be at least 30 days. The patient's physician may determine that anticoagulation therapy should be continued after the study period, based on their examination of the patient at the 30-day post-operative examination.

Warfarin should not be used if a patient has active pathological bleeding.

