5.4.1 Dose Modifications

Apixaban: in patients with at least 2 of the following characteristics, age ≥ 80 years, body weight ≤ 60 kg, or serum creatinine ≥ 1.5 mg/dL (133 $\mu\text{mol/L}$), the recommended dose of apixaban is 2.5 mg twice daily.

Warfarin: doses of warfarin will be determined on a daily basis while the patient is in the hospital. After discharge from the hospital, after each INR check, a pharmacist or nurse will contact the patient to communicate the appropriate dosing.

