5.7 Treatment Compliance

Patient compliance will be monitored during the study. While the patient is hospitalized, we will monitor whether apixaban or warfarin is given as directed by the study coordinator. After the patient has been discharged from the hospital, apixaban compliance will be measured by asking the patient to bring any unused medication to their 30-day post-operative appointment, where remaining tablets will be counted. As 60 tablets will be dispensed to each patient (30-day supply), we use the following formula:

$$[(60 - (\text{\# of remaining tablets})) * 100] / [2 * (\text{days since filled})] = \text{percent compliance.}$$

After hospital discharge, warfarin compliance will be monitored by measuring the time in therapeutic INR range (2-3).

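### Section 6.4.2 divides apixaban doses by days prescribed, so it gives exactly twice the section 2.1 compliance value and up to 200%; one formula should be stated in 2.1, 5.7 and 6.4.2.

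*Combined protocol and SAP*

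**What the plan says.** The synopsis lists "patient compliance percentage to apixaban if on apixaban" among the secondary endpoints, and section 6.4.2 repeats it as item 5. The calculation appears in three places:

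- **Section 2.1, item 7:** "Patient compliance percentage to apixaban dosing, calculated as a percentage using the following equation". Doses not taken and returned are subtracted from doses prescribed, and the result is divided by doses prescribed. It adds that "the follow up visit will occur after anticoagulation prescription has ended".
- **Section 5.7:** "As 60 tablets will be dispensed to each patient (30-day supply), we use the following formula". Sixty minus the remaining tablets, times 100, is divided by twice the days since filling.
- **Section 6.4.2, item 5:** the numerator of 2.1 with a different divisor: "of doses not taken and returned to investigator at follow up appointment) / # days prescribed". The result is still described as a percentage.

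Dosing is twice daily at both levels: section 5.4 has "Apixaban is to be dosed at 5 mg by mouth twice daily", and for the reduced dose section 5.4.1 has "the recommended dose of apixaban is 2.5 mg twice daily". The section 6.1 schedule marks dispensing at hospital discharge. Sections 5.7 and 6.4.2 place the tablet count at the 30-day visit after surgery.

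**The concern.** A compliance percentage should compare doses taken with doses that were to be taken. Section 6.4.2 compares doses with days. For a twice-daily drug that doubles the answer.

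The reported value then depends on which section the analyst follows. A result near 200% would be noticed. The less obvious risk lies lower down: a patient who took between a quarter and a half of the prescribed doses scores between 50% and 100% under 6.4.2, which looks plausible and is twice the 2.1 value.

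**Working it through.** **Inputs.** Two doses a day (5.4, 5.4.1); 60 tablets dispensed as a 30-day supply (5.7). Supply check: 2 × 30 = 60, so the plan's own figure is reproduced and one tablet is one dose.

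**Notation.** P = doses prescribed, D = days prescribed, r = doses returned, d = days from filling to the count.

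- 2.1: 100 × (P − r) / P
- 6.4.2: 100 × (P − r) / D
- 5.7: 100 × (60 − r) / (2d)

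**Step 1: 6.4.2 against 2.1.** Twice-daily dosing gives P = 2D. So 6.4.2 = 100 × (P − r) / (P/2) = 2 × the 2.1 value, whatever P is. With r = 0 it gives 200%. It exceeds 100% whenever more than half of the prescribed doses count as taken. With P = 60 and D = 30:

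| Taken of 60 | 2.1 | 6.4.2 |
|---|---|---|
| 60 | 100% | 200% |
| 54 | 90% | 180% |
| 45 | 75% | 150% |
| 30 | 50% | 100% |

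The rows use P = 60; the 2:1 ratio and the 200% ceiling do not depend on it.

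**Step 2: 2.1 against 5.7, which depends on the reading.** *Assumption:* doses prescribed means the 60 dispensed. Then, for anyone who took a tablet, 2.1 / 5.7 = 2d/60 = d/30, which equals 1 only at d = 30. For a patient who missed nothing and returns the unused 60 − 2d tablets, 5.7 gives 100% and 2.1 gives 100 × d/30. The documents give no discharge day or visit window, so d is assumed:

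| d (assumed) | 2.1 | 5.7 |
|---|---|---|
| 20 | 66.7% | 100% |
| 24 | 80.0% | 100% |
| 28 | 93.3% | 100% |
| 30 | 100% | 100% |

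Each day short of 30 costs 2/60 = 3.3 points under 2.1.

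*Other reading:* doses prescribed means the 2d doses due since filling, and only due doses that were missed (m) are subtracted. Then 2.1 = 100 × (2d − m)/(2d). In 5.7 the remaining tablets are 60 − 2d + m, so its numerator is also 2d − m. The two formulas agree.

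**Step 3: where 5.7 itself needs care (illustrative timings).**

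- Prescription ends 24 days after filling, count at day 26, nothing missed: 5.7 gives 4800/52 = 92.3%. Counting only the 48 doses due gives 4800/48 = 100%.
- All 60 tablets used by day 30, count at day 35: 5.7 gives 6000/70 = 85.7%. Stopping at the end of the supply gives 6000/60 = 100%.
- Nothing brought back, count at day 26: 6000/52 = 115%. At least 60 − 52 = 8 tablets cannot be explained by scheduled use.

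**The case against.** The strongest reply is that this is one wrong word. The numerators of 2.1 and 6.4.2 match, so *days* is probably a slip for *doses*; with it corrected the two are one formula. Scores of 180% to 200% would expose the error. No sample size or between-arm test uses the endpoint, and section 10.2.2 requires logs of the amounts dispensed and returned, so the values can be recalculated. All of this stands and limits the weight of the point. It does not make the written rule right.

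A reader might infer that the plan holds three rival formulas with no hint of which is meant. That goes too far. Section 5.7 is the section on compliance and says that its formula is the one used. Section 6.1, which follows it, exempts compliance from the record-based analysis by referring back to earlier text, most naturally 5.7. But that reference names no equation, and 6.4.2 then states its own. The documents favour 5.7 without settling the matter.

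A reader might also infer that 2.1 counts doses not yet due as missed. That requires doses prescribed to mean the 60 dispensed and the count to come before those doses fall due. Section 2.1 itself puts the visit after the end of the prescription, which weakens that reading. The documents do not establish it.

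**Conclusion.** The point holds for section 6.4.2. As written, its formula returns exactly twice the 2.1 value and can reach 200%. This rests only on twice-daily dosing and on the same prescribed period being used in numerator and denominator; partial first or last days would shift the ratio slightly.

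The difference between 2.1 and 5.7 is conditional. On one reading of doses prescribed it can be large (66.7% against 100% at an assumed 20 days); on the other it vanishes. It is a reason to define the term, not a second demonstrated error.

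The consequence is minor: one descriptive endpoint in the apixaban arm (28 patients planned), with no bearing on the efficacy or bleeding comparisons. It should still be corrected before analysis, because the choice of formula would otherwise be made with the data in hand.

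**What to change.** Correct the 6.4.2 denominator and state one formula, based on 5.7, in sections 2.1, 5.7 and 6.4.2:

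100 × (tablets dispensed − tablets returned) / (doses due from filling to the earliest of the count, the end of the apixaban prescription, or the end of the dispensed supply).

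The end of supply is the scheduled run-out, 60/2 = 30 days after filling. With nothing missed, counts at day 20, 26, 30 or 35 all give 100%; with half of the due doses taken at day 20, the result is 20/40 = 50%.

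Two additions are needed:

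- Record tablets not brought back as unaccounted for, instead of counting them automatically as taken, and report how many there are. Otherwise the formula can still exceed 100%.
- Reconcile the formula with the 2.1 statement that the visit follows the end of the prescription. Section 4.1 runs treatment up to the 30-day visit, and section 5.4 sets a minimum of 30 days with possible continuation. These passages must be made consistent; no dose or treatment duration is proposed here.

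The cost is low: wording in three sections. Dispensed and returned amounts are already logged under 10.2.2, and 5.7 already needs the fill date. The only new items are the prescription end date, when it precedes the count, and an entry for unaccounted tablets.

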9	STATISTICAL CONSIDERATIONS.....	38
9.1	Sample Size DeterminationError! Bookmark not defined.	36
9.2	Populations for Analyses	38
9.3	Analyses	36
10	STUDY MANAGEMENT	39
10.1	Compliance with the Protocol.....	39
10.2	Records Retention	40
10.2.1	Records Retention	40
10.2.2	Study Drug Records.....	40
10.3	Destruction of Investigational Product.....	41
11	GLOSSARY OF TERMS.....	42
12	LIST OF ABBREVIATIONS	43
13	REFERENCES.....	44

PROTOCOL SYNOPSIS

Protocol Title:	Apixaban versus warfarin for the management of post-operative atrial fibrillation: a prospective, controlled, randomized pilot study
Site Numbers & Names:	Sanford Medical Center, Fargo, ND
Research Hypothesis:	We hypothesize that there will be no significant differences between apixaban and warfarin anticoagulation strategies for the outcomes of venous thromboembolism/stroke or bleeding events when utilized for new-onset postoperative atrial fibrillation after isolated coronary artery bypass grafting (CABG).
Study Schema: Drugs / Doses / Length of Treatment)	
Patients who develop persistent atrial fibrillation after isolated coronary artery bypass grafting will be identified and randomized to anticoagulation with either warfarin (standard of care) or apixaban.
 
Warfarin will be dosed daily, with International Normalized Ratio (INR) monitoring per hospital protocol. After discharge, warfarin dosing will be managed by the anticoagulation clinic per protocol with a target INR of 2-3.
 
Apixaban will be dosed at 5 mg twice daily, or 2.5 mg twice daily in patients with at least two of the following characteristics: age \geq 80 years, weight \leq 60 kg, or serum creatinine \geq 1.5 mg/dL.
 
Patients will remain on anticoagulation until no longer needed (typically within 30 days of surgery). Study follow-up will be through the patient's 30-day follow-up appointment.

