5.4.2 Temporary Discontinuation of Apixaban or Warfarin

Discontinuing anticoagulants, including apixaban or warfarin, for active bleeding, elective surgery, or invasive procedures places patients at an increased risk of thrombosis. Lapses in therapy should be avoided, and if anticoagulation with apixaban and warfarin must be temporarily discontinued for any reason, therapy should be restarted as soon as possible.

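### Apixaban compliance can count doses withheld on instruction as missed and unused tablets not brought back as taken, and no rule covers either patient

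*Combined protocol and SAP*

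**What the plan says.** Compliance with apixaban is a secondary endpoint in the synopsis and in section 6.4.2 (item 5), and is also listed under the Primary Objective heading in 2.1 (item 7). Three formulas are given.

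- **2.1:** doses prescribed, less the number "of doses not taken and returned to investigator at follow up appointment", divided by doses prescribed. It adds that "the follow up visit will occur after anticoagulation prescription has ended".
- **6.4.2:** the same numerator, divided by days prescribed.
- **5.7:** "As 60 tablets will be dispensed to each patient (30-day supply), we use the following formula": 60 minus remaining tablets, times 100, over twice the "days since filled". The count comes from "asking the patient to bring any unused medication to their 30-day post-operative appointment, where remaining tablets will be counted".

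The plan foresees that therapy may stop early or be interrupted. The synopsis says "Patients will remain on anticoagulation until no longer needed (typically within 30 days of surgery"). Section 5.4.2 says "if anticoagulation with apixaban and warfarin must be temporarily discontinued for any reason, therapy should be restarted as soon as possible". Section 4.2.4 lists reasons for mandatory discontinuation, 5.6.2 describes holds before procedures, and 6.1 mentions stops for safety.

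The nearest thing to a handling rule is in 4.2.4, where an incomplete course, or failure to take medication, is to be noted. The drug records in 10.2.2 log amounts returned, lost or wasted. Neither enters any of the three formulas.

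**The concern.** A compliance figure should compare tablets taken with tablets the patient was under instruction to take. Two gaps get in the way.

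First, 5.7 divides by calendar time since the fill. Days on which the patient was told not to take apixaban stay in the denominator, so a patient who did as instructed looks non-compliant. Sections 2.1 and 6.4.2 have the same effect if *doses prescribed* and *not taken* are read literally.

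Second, 2.1 and 6.4.2 deduct only what comes back. Unused tablets left at home or thrown away are credited as taken. Section 5.7 does the same if a patient who brings nothing is entered as having none remaining. No study calls are added after discharge (4.1) and no assessment follows the 30-day examination (6.1), so the plan specifies no step to recover a missing count.

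At stake is the main planned quantitative measure of post-discharge adherence in an arm of 28, in a pilot that section 9.1 offers as a reference for later studies.

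**Working it through.** **Inputs from the plan.** 60 tablets per patient, twice-daily dosing, a 30-day supply (5.7, 5.4); 28 patients per arm (4.1); dispensing at hospital discharge and tablet count at the 30-day visit (6.1). Check on the plan's one constant: 2 × 30 = 60, which agrees.

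**Assumed, because not stated.** Discharge on day 5 to 10 with the visit on day 30 gives D = 25 to 20 days since the fill; D = 30 is shown where noted. Doses prescribed P = 60 unless noted. R is the number of tablets brought back.

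**Formulas.** 2.1: 100(P − R)/P. 5.7: 100(60 − R)/(2D). 6.4.2: 100(P − R)/days prescribed.

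**Patient 1: every dose taken until an instructed stop 14 days after the fill, all leftovers returned.** Taken 28, R = 32, adherence to instruction 100%.
- 5.7: 28/50 = 56% at 25 days; 28/40 = 70% at 20 days.
- 2.1, literal: 28/60 = 47%.
- 6.4.2, literal: 28/30 = 93%, on a scale where full adherence reads 60/30 = 200%.
- 2.1 with P cut to the 28 doses due but all 32 tablets still deducted: (28 − 32)/28 = −14%. Shortening *prescribed* alone does not repair it; the leftovers must also be kept out of *not taken*.

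**Patient 2: a two-day instructed hold, otherwise every dose taken, D = 30.** R = 4. Both 2.1 and 5.7 give 56/60 = 93% instead of 100%.

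**Patient 3: brings no unused tablets, whatever was taken.** R = 0.
- 2.1: 60/60 = 100%.
- 5.7, if entered as zero remaining: 60/60 = 100% at 30 days, 60/50 = 120% at 25, 60/40 = 150% at 20. No cap or query is stated.
- For comparison, a perfect adherer at 25 days returns 10 tablets and scores 50/60 = 83% by 2.1, below the patient who brought nothing.

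**Arm mean, n = 28 (illustration only).** Assume 2.1 or 5.7 at D = 30; most patients at 90%; non-returners truly 50% but scored 100%; patients stopped on instruction at day 15 truly 100% but scored 50%.

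| Non-returners | Instructed stops | True mean | Scored mean | Difference (points) |
|---|---|---|---|---|
| 3 | 0 | 2400/28 = 85.7% | 2550/28 = 91.1% | +5.4 |
| 6 | 0 | 2280/28 = 81.4% | 2580/28 = 92.1% | +10.7 |
| 0 | 6 | 2580/28 = 92.1% | 2280/28 = 81.4% | −10.7 |
| 6 | 6 | 2340/28 = 83.6% | 2340/28 = 83.6% | 0 |

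The direction also depends on the formula and on the time since the fill. Assume 4 non-returners truly at 60% and 24 others at 90%: the true mean is (24 × 0.90 + 4 × 0.60)/28 = 85.7%. At 25 and 20 days:
- 5.7 gives (21.6 + 4 × 1.20)/28 = 94.3% and (21.6 + 4 × 1.50)/28 = 98.6%.
- 2.1 scores each of the 24 at 45/60 = 75% or 36/60 = 60%, because tablets not yet due count as missed. The mean is (24 × 0.75 + 4)/28 = 78.6% or (24 × 0.60 + 4)/28 = 65.7%, below the truth.

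**The case against.** The best defence concerns the wording of 2.1 and 6.4.2. They speak of doses or days *prescribed*, and 2.1 places the visit after the prescription ends. If a physician's stop ends the prescription, and if *prescribed* and *not taken* both cover only doses the patient was told to take, the stop error disappears from those two formulas. That reading is possible but unstated, and it cannot rescue 5.7, whose denominator is calendar time. So a reader should not infer that all three formulas certainly fail in both directions: the stop error is unambiguous only in 5.7.

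Likewise, 5.7 counts tablets at the visit. A missed visit yields no count, and the text does not say that it becomes zero. The upward error there is conditional; in 2.1 and 6.4.2 it follows from the wording.

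Four further inferences are tempting and should not be drawn:
- *That arm-level compliance will be overstated.* No event frequency is given, and the worked means go both ways.
- *That the 200% from 6.4.2 measures this problem.* It is that formula's doses-over-days unit error and needs its own correction.
- *That the tablet count is the only adherence evidence.* In-hospital administration is monitored (5.7), failure to take medication is noted (4.2.4) and the drug log exists (10.2.2).
- *That efficacy and safety results would be misread.* Analysis is by intention to treat (9.3), no compliance-adjusted analysis is planned, and reasons for stopping are documented (4.2.4, 6.1).

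It can also be said that this is the familiar weakness of any pill count. That is partly so for discarded tablets. It does not cover a denominator that ignores instructed holds, or the absence of a rule for a patient with no count, both of which text can cure.

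**Conclusion.** The point holds at patient level. Section 5.7 gives wrong values to patients whose apixaban is held or stopped on instruction, an event the plan itself foresees; 2.1 and 6.4.2 do so on a literal reading. Sections 2.1 and 6.4.2 credit unreturned tablets as taken, and 5.7 does if nothing brought is entered as zero.

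For the affected patient the error is large: about 30 to 44 points down by 5.7 for a day-14 stop, and any shortfall at all can be hidden for a patient who brings nothing. These figures rest on 60 prescribed doses and an assumed 20 to 25 days from fill to visit. At arm level, neither the size nor the sign can be stated from the documents.

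The consequence is limited to a descriptive secondary measure in one arm. It is worth correcting because the correction is cheap and, with 28 patients, a few wrong values move the mean by several points.

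**What to change.** Keep one formula and state it identically in 2.1, 5.7 and 6.4.2:

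1. **Numerator:** tablets dispensed minus tablets counted.
2. **Denominator:** doses due from the fill to the earlier of the visit or the documented instructed stop, less doses held on instruction. Patient 1 then scores 28/28 = 100% and Patient 2 scores 56/56 = 100%.
3. **No count:** compliance is missing if the visit was missed or unused tablets were not brought. Record zero remaining only when the patient confirms or shows that the supply is finished. A rule based on whether a bottle came back would not do: patients are asked only for unused medication, so someone who had finished the supply would be set to missing.
4. **Reporting:** give the number missing and bound the arm mean by setting missing values to 0% and then 100%. With 4 of 28 missing and the rest at 90%, the bounds are 21.6/28 = 77.1% and 25.6/28 = 91.4%.
5. **Values above 100%:** query them before they enter a mean.
6. **Data:** record stop and hold dates for this purpose. The plan documents reasons for stopping, and 6.1 leaves compliance out of the EMR outcome review, so these dates cannot be assumed to be collected.

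Before the denominator is fixed, the sponsor must reconcile the synopsis (therapy until no longer needed), 4.1 (30 days, continuing to the visit) and 5.4 (at least 30 days), together with the statement in 2.1 that the visit follows the end of the prescription.

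The cost is one paragraph repeated in three sections and some abstraction of dates. The downside is that some patients will have a missing value. Tablets discarded by a patient who returns others will still go undetected.
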